1.2.2.2 Summary of Clinical Data

In the current clinical development program (as of November 12th, 2022), ibrutinib is being evaluated in over 72 ongoing and completed company-sponsored clinical studies in healthy subjects and in subjects with recurrent B-cell lymphomas, including CLL/SLL, MCL, follicular lymphoma (FL), DLBCL, multiple myeloma (MM), WM, marginal zone lymphoma (MZL), AML, chronic GvHD and solid tumors. Safety data from completed studies are available for 2326 subjects treated with single-agent ibrutinib and for 3447 subjects treated with ibrutinib in combination with immunotherapy or chemoimmunotherapy (5,261 subjects with hematologic malignancies, cGVHD, or solid tumors, 460 healthy volunteers, 22 subjects with COVID-19 related pulmonary distress, and 30 subjects from a hepatic impairment study). In addition, 9 early access programs are ongoing or completed and 201 initiated-studies including 43 collaborations are ongoing or completed.

The exposure-response analysis of Study MCL3002 on safety showed that there was no association between systemic exposure and the incidence of major hemorrhage, liver function abnormalities (Grade ≥ 3), neutropenia, diarrhea (Grade ≥ 2), TEAEs leading to death, or TEAEs leading to ibrutinib dose reduction. An effect of ibrutinib versus placebo treatment was observed on TEAEs leading to ibrutinib discontinuation, all Grade ≥ 3 TEAEs, all serious TEAEs, Afib (any), any hemorrhage, and infection (Grade ≥ 3). Of these, only Afib (any) and any hemorrhage showed a significant exposure response relationship with $AUC_{\tau,ss}$ within the exposure range obtained in the ibrutinib treatment arm.

Description of Investigational Drug Product and Pharmacokinetics

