Ibrutinib is available as 140 mg capsules. Following oral administration of ibrutinib at doses ranging from 420 to 840 mg/day, exposure to ibrutinib increased proportionally to doses increased with substantial intersubject variability. Administration of ibrutinib in a fasted condition resulted in approximately 60% of exposure (area under the plasma concentration-time curve from time zero to the time of the last quantifiable concentration [AUClast]) as compared to administration either in fed condition (30 minutes after a high-fat breakfast), or when drug was taken 30 minutes before or 2 hours after a meal. Based on data for the effects of food, ibrutinib could be taken with or without food at approximately the same time each day. Ibrutinib absorption from the GI tract is practically complete, as minimal fecal excretion of unchanged ibrutinib in combination with high levels of oxidative metabolites (liver and gut metabolism) and a lack of reduction products (gut microflora metabolism) was observed in the human mass balance study. Ibrutinib is extensively metabolized, as evidenced by a human mass balance study in 6 male subjects dosed with a single 140-mg ibrutinib solution admixed with [¹⁴C]-ibrutinib.

Ibrutinib is predominantly cleared by 3 primary cytochrome P450 (CYP) 3A-mediated metabolic pathways, one of them being epoxidation of the acryloyl moiety, followed by hydrolysis to form the dihydrodiol PCI-45227. The two other main pathways are hydroxylation of the distal phenyl moiety and oxidative piperidine ring opening. The mean half-life ($t_{1/2}$) of ibrutinib ranged from 4 to 13 hours, with a median time to maximum plasma concentration (Tmax) of 2 hours.

Excretion is predominantly via the feces with approximately 80% recovered mostly within 2 days, whereas ~8% was excreted in urine. Approximately 1% of ibrutinib was recovered as unchanged drug, all in feces. Intravenous clearance as determined in an absolute bioavailability study was 62 and 76 L/h in fasted and fed condition, respectively. In line with the high first-pass effect, the apparent oral clearance is much higher, in the order of 2000 and 1000 L/h in fasted and fed condition, respectively. Overall, these PK characteristics resulted in minimal accumulation of both parent compound and metabolite PCI-45227 on repeated daily dosing of ibrutinib. Steady state exposure of ibrutinib and PCI-45227 was less than 2-fold of first dose exposure.

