A hepatic impairment study was performed in non-cancer subjects administered a single dose of 140 mg ibrutinib under fasting conditions. Ibrutinib AUC last increased 2.7-, 8.2- and 9.8-fold in subjects with mild (n=6; Child-Pugh Class A), moderate (n=10; Child-Pugh Class B) and severe (n=8; Child-Pugh Class C) hepatic impairment, respectively ([Appendix J](#)). The free fraction of ibrutinib also increased with degree of impairment, with 3.0%, 3.8%, and 4.8% in subjects with mild, moderate, and severe liver impairment, respectively, compared to 3.3% in plasma from matched healthy controls within this study. The corresponding increase in unbound ibrutinib exposure is estimated to be 4.1-, 9.8-, and 13-fold in subjects with mild, moderate and severe impairment, respectively.

Hematologic Malignancies

Pooled safety data from a total of 1,600 subjects treated with ibrutinib monotherapy in 21 studies that have completed primary analysis or final analysis included in the CSR as of the 12 November 2022 cutoff date for the current IB update are summarized below.

The most frequently reported treatment-emergent adverse events (TEAEs) in subjects receiving ibrutinib as monotherapy (N = 1,600):

Any grade TEAE >10% ^a	Any grade TEAEs related to ibrutinib > 5% ^a	Grade 3 or 4 TEAEs > 2% ^a
Diarrhea	Diarrhea	Diarrhea
Fatigue	Fatigue	Fatigue
Nausea	Nausea	Anemia
Cough	Cough	Neutropenia
Pyrexia	Pyrexia	Thrombocytopenia
Anemia	Anemia	Pneumonia
Upper Respiratory Tract Infection	Upper Respiratory Tract Infection	Hypertension
Neutropenia	Neutropenia	Urinary tract infection
Edema peripheral	Thrombocytopenia	Atrial fibrillation
Thrombocytopenia	Muscle spasms	Febrile neutropenia

Abbreviated Title: Ibrutinib for Chronic GvHD**Version Date: 4/26/2023**

Any grade TEAE >10% ^a	Any grade TEAEs related to ibrutinib > 5% ^a	Grade 3 or 4 TEAEs > 2% ^a
Muscle spasms	Constipation	Hypokalemia
Constipation	Arthralgia	Hyponatremia
Arthralgia	Vomiting	Abdominal pain
Vomiting	Decrease in appetite	Cellulitis
Decrease in appetite	Pneumonia	Neutrophil count decreased
Dyspnea	Rash	
Headache	Stomatitis	
Pneumonia	Increased tendency to bruise	
Rash	Platelet count decreased	
Hypertension		
Abdominal pain		
Back pain		
Contusion		
Dizziness		
Urinary tract infection		
Sinusitis		

^a Source is Table 5 of IB (v16).

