- 2.1.2.8 Active hepatitis C virus (HCV) or hepatitis B virus (HBV). Subjects who are positive for hepatitis B core antibody or hepatitis B surface antigen or hepatitis C antibody must have a negative polymerase chain reaction (PCR) result to be enrolled.
- 2.1.2.9 Known hypersensitivity to ibrutinib
- 2.1.2.10 Pregnant women are excluded from this study because ibrutinib has potential for teratogenic and abortifacient effects. Because there is an unknown but potential risk for adverse events in nursing infants secondary to treatment of the mother with ibrutinib, breastfeeding should be discontinued if the mother is treated with ibrutinib. Women who are planning to become pregnant and men who plan to father a child while enrolled in this study or \leq 30 days after the last dose of study drug are excluded.
- 2.1.2.11 Any other reason at the discretion of the investigators and documented in the medical record that may raise concerns about the subject safety or ability to participate on this study
- 2.1.2.12 Currently active, severe hepatic impairment Child-Pugh class C according to the Child Pugh classification ([Appendix J](#))

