3 STUDY IMPLEMENTATION

3.1 STUDY DESIGN

This is a multi-center, two-stage, phase 2 study.

Subjects with newly diagnosed moderate or severe chronic GvHD according to the NIH criteria, who need systemic therapy, will be started on ibrutinib as a continuous daily dose of 420 mg by mouth. Treatment will continue in cycles consistent of 28 days on outpatient basis.

Participants with response at 6 months (CR+PR) will continue therapy until 12 months.

Participants who have a perception of benefit from ibrutinib therapy may continue on ibrutinib past the 12-month timepoint, based also on investigator discretion and discussion for up to 24 months.

Subjects may continue on stable doses of their immunosuppressive medications with the intent to taper it. See Section [4.1](#).

Addition of any systemic immunosuppressive therapy aimed at controlling chronic GvHD symptoms is prohibited and will be considered treatment failure. Participants in need of additional systemic immunosuppressive therapy will be taken off ibrutinib treatment.

Subjects may remain on topical therapy for chronic GvHD (See Section [4.2](#)).

Abbreviated Title: Ibrutinib for Chronic GvHD

Version Date: 4/26/2023

One steroid pulse (i.e., prednisone equivalent of 0.5-2 mg/kg/day) is allowed (See Section [4.1.2](#)).

Up to 28 evaluable subjects will be enrolled and treated for up to 24 months. Enrollment will occur in 2 stages: in the first stage 14 subjects will be enrolled, and if ≥ 4 subjects have a response (CR+PR at 6 months) the accrual will continue until a total of at least 25 evaluable subjects have been enrolled. As it may take 3 to 6 months to determine if a subject has experienced a response, a temporary pause in the accrual may be necessary to ensure that enrollment to the second stage is warranted.

Evaluation of chronic GvHD diagnosis per NIH criteria ([Appendix A](#)) and Chronic GvHD Organ Specific Staging and Global Scoring ([Appendix D](#) and [Appendix E](#)) will be performed at screening. Chronic GvHD Organ Specific Staging and Global Scoring ([Appendix D](#) and [Appendix E](#)) evaluations will be repeated at 9 months and 12 months, and every 3 months until off treatment.

Chronic GvHD Activity Assessment (Clinician) Form A ([Appendix F](#)) will occur at baseline, at 6 weeks and then 3, 6, 9 and 12 months from the start of ibrutinib by the bone marrow transplant physician and/or nurse practitioner trained in chronic GvHD assessments.

[figure not shown]

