Second	Withhold ibrutinib until recovery to Grade ≤ 1 or baseline; may restart at 1 dose level below that for which the toxicity occurs
Third	Withhold ibrutinib until recovery to Grade ≤ 1 or baseline; may restart at 1 dose level below that for which the toxicity occurs
Fourth	Discontinue ibrutinib

3.3.2.2 Dose modification for atrial fibrillation:

For Grade 3 or 4 atrial fibrillation or persistent atrial fibrillation of any grade, consider the risks and benefits of ibrutinib treatment. If clinically indicated, the use of anticoagulants or antiplatelet agents may be considered for the thromboprophylaxis of atrial fibrillation.

3.3.2.3 Dose modifications for hepatic impaired subjects:

- Ibrutinib is metabolized in the liver and therefore subjects with clinically significant chronic hepatic impairment at the time of Screening (Child- Pugh class C) are excluded from study participation. Refer to [Appendix J](#) for Child-Pugh classification. For subjects with a direct bilirubin $> 3 \times$ ULN (Grade 3 CTCAE), ibrutinib will be held until the bilirubin returns to $\leq 1.5 \times$ ULN (Grade 1 CTCAE) or baseline. Upon reduction to $\leq 1.5 \times$ ULN ibrutinib will be re-started at one dose level below that for which the toxicity occurs (see [Table 1](#) for dose modification schedule).
- For subjects whose baseline AST/ALT is $\leq 3 \times$ ULN, if ALT or AST increases to $> 5 \times$ ULN (Grade 3 CTCAE) ibrutinib will be held until the ALT/AST value returns to $\leq 3 \times$ ULN (Grade 1 CTCAE) or baseline. Ibrutinib will be re-started at one dose level below that for which the toxicity occurs.
- For subjects whose baseline AST/ALT is between 3 to 5 \times ULN (because of chronic GvHD), if ALT/AST increases to 1.5 \times baseline level then ibrutinib will be held until the ALT/AST value returns to $\leq 3 \times$ ULN or baseline. Ibrutinib will be re-started at one dose level below that for which the toxicity occurs.

Table 1: Ibrutinib Dose Modifications for Hepatic Impairment

Occurrence	Action to be Taken
------------	--------------------

First	Withhold study drug until recovery to Grade ≤ 1 CTCAE or baseline; restart at 1 dose level below that for which the toxicity occurs (280 mg/day for 420 mg/day dose)
Second	Withhold study drug until recovery to Grade ≤ 1 CTCAE or baseline; restart at 1 dose level below that for which the toxicity occurs 140 mg/day for 280 mg/day dose)
Third	Discontinue study drug

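### Child-Pugh class B participants can enrol and start at the full 420 mg, although the protocol's own pharmacokinetic data put their exposure about 8-fold above normal

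*Combined protocol and SAP*

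**What the plan says.** Section 2.1.2.12 excludes "Currently active, severe hepatic impairment Child-Pugh class C according to the Child Pugh classification". Section 3.3.2.3 gives the reason: "Ibrutinib is metabolized in the liver and therefore subjects with clinically significant chronic hepatic impairment at the time of Screening", a group it equates with class C, are kept out. Class B is not mentioned in either place.

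Section 1.2.2.2 describes a hepatic impairment study: "Ibrutinib AUC last increased 2.7-, 8.2- and 9.8-fold in subjects with mild", moderate and severe impairment (classes A, B and C; n = 6, 10 and 8). The corresponding "increase in unbound ibrutinib exposure is estimated to be 4.1-, 9.8-, and 13-fold". The data come from a single fasted 140 mg dose in subjects without cancer.

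Under section 3.1, participants "will be started on ibrutinib as a continuous daily dose of 420 mg by mouth"; section 3.2 agrees. The dosing table in section 3.2.1 lowers the starting dose only for voriconazole (280 mg) and posaconazole (280 or 140 mg). The dose rules in section 3.3.2.3 and Table 1 are triggered by bilirubin or transaminase rises during treatment. They set no starting dose.

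**The concern.** The stated reason for the exclusion is hepatic metabolism, and the protocol's own figures show that this reason reaches well into class B. The large step in exposure lies between class A (2.7-fold) and class B (8.2-fold), while the protocol draws its line between B and C (9.8-fold). A class B participant managed exactly as written would take the full dose from day 1, with no rule that responds to liver function until a liver test worsens.

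What is at stake is participant safety. The primary endpoint, the two-stage rule and the analysis are unaffected. Section 1.2.2.2 reports, from one study in mantle cell lymphoma, that "only Afib (any) and any hemorrhage showed a significant exposure response relationship" with steady-state AUC among the events for which an ibrutinib effect was seen. That finding is confined to the exposure range of that study's ibrutinib arm.

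**Working it through.** **Inputs.** Fold changes and free fractions (3.0%, 3.8% and 4.8% in classes A, B and C; 3.3% in controls): section 1.2.2.2. Doses: sections 3.1, 3.2 and 3.2.1. Highest cited doses (1400 mg/day with no maximum tolerated dose reached; 1680 mg as a single dose, after which one healthy subject had reversible Grade 4 AST and ALT increases): end of section 1.2.2.1. Bilirubin limit of 3 x ULN: section 2.1.1.7. Scoring: Appendix J.

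**1. The plan's own figures.** The total AUC folds are observed results and cannot be rebuilt from the documents. The unbound folds can be approximated as AUC fold x free fraction / 3.3:
- A: 2.7 x 3.0/3.3 = 2.45 (stated 4.1)
- B: 8.2 x 3.8/3.3 = 9.44 (stated 9.8)
- C: 9.8 x 4.8/3.3 = 14.25 (stated 13)

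These do not match exactly. The stated values may rest on individual-level estimates, so both sets are carried forward.

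**2. Class B as a share of class C.**
- Total AUC: 8.2/9.8 = 84%
- Unbound, as stated: 9.8/13 = 75%
- Unbound, recomputed: 9.44/14.25 = 66%

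**3. Can class B enrol?** Bilirubin of 2-3 mg/dL (2 points) and albumin of 2.8-3.5 g/dL (2), with the other three items normal (1 each), score 2 + 2 + 1 + 1 + 1 = 7, which is class B. With an assumed bilirubin ULN of 1.0 to 1.3 mg/dL, the entry limit is 3.0 to 3.9 mg/dL, so this participant passes. Where the ULN exceeds 1.0 mg/dL, bilirubin above 3 mg/dL can also pass, and it reaches class B alone: 3 + 1 + 1 + 1 + 1 = 7. Section 2.1.1.7 sets no limit on albumin or INR, and neither ascites nor encephalopathy has its own eligibility criterion.

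**4. Exposure relative to 420 mg with a normal liver** = (dose/420) x fold:

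| Class B daily dose | Total AUC, fold 8.2 | Fold halved, 4.1 | Unbound, fold 9.8 |
|---|---|---|---|
| 420 mg | 8.2 | 4.1 | 9.8 |
| 280 mg | 5.5 | 2.7 | 6.5 |
| 140 mg | 2.7 | 1.4 | 3.3 |

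Class A at 420 mg, which the protocol accepts, has 2.7 times on total AUC. On unbound drug, class B at 140 mg is lower than class A at 420 mg with the stated figures (3.27 against 4.1) and higher with the recomputed ones (9.44/3 = 3.15 against 2.45).

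**5. Normal-liver dose equivalent** = dose x fold:
- Class B, 420 mg: 420 x 8.2 = 3444 mg, which is 2.46 times 1400 mg and 2.05 times 1680 mg
- Fold halved: 420 x 4.1 = 1722 mg, still above both cited doses
- Class B, 140 mg: 140 x 8.2 = 1148 mg; on the unbound fold, 140 x 9.8 = 1372 mg; both below 1400 mg
- Class A, 420 mg: 420 x 2.7 = 1134 mg

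Matching the intended exposure exactly would need 420/8.2 = 51 mg, less than one 140 mg capsule.

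**6. What would act before or soon after the first dose?** The holds in section 3.3.2.3 need direct bilirubin above 3 x ULN, or transaminases above 5 x ULN (or 1.5 times a raised baseline). Stable class B disease need trigger none of these. The pharmacokinetic sample is taken at C1D15, two weeks after starting, and may be shipped only at the end of the trial.

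**The case against.** Several counter-arguments have force.

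- **Frequency.** Liver involvement in chronic GvHD does not imply class B. Child-Pugh scoring uses no transaminases, so the enzyme-only disease admitted up to 5 x ULN adds no points. This stands: the documents give no basis for estimating how many class B participants would enrol.
- **Harm.** Section 1.2.2.2 says "there was no association between systemic exposure and the incidence of major hemorrhage", and likewise none for Grade 3 or higher liver abnormalities or for adverse events leading to death. No maximum tolerated dose was reached up to 1400 mg/day. This stands as far as it goes, but neither result reaches an exposure equivalent to 3444 mg, or even 1722 mg.
- **Transport.** The folds come from 10 class B subjects given one fasted dose, and a GvHD patient who scores class B may differ. Proportionality is supported only in that "at doses ranging from 420 to 840 mg/day, exposure to ibrutinib increased proportionally". This limits precision; halving the fold still leaves 4.1 times the intended exposure.
- **Discretion.** Investigators may exclude on safety grounds (2.1.2.11) or reduce the dose for bothersome toxicity (3.3.2), and the précis asks for adequate hepatic function. None of these sets a class B threshold or a starting dose, and reduction for toxicity follows exposure.
- **Azole comparison.** The protocol gives no fold increase for any inhibitor and keeps moderate inhibitors at 420 mg. The azole doses therefore show that starting-dose cuts are an accepted tool, but they cannot calibrate one for class B.

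A reader might infer that class B is effectively class C and must be excluded. The documents do not support that. On unbound drug class B has 66-75% of the class C value, and a blanket exclusion could override the 3 x ULN bilirubin limit and remove liver-GvHD patients whom the trial admits and whose liver response it measures.

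**Conclusion.** The concern holds as a should-fix point on participant safety. Following the protocol as written gives a class B participant roughly 4 to 8 times the intended total exposure, and 9.8 times on the stated unbound figure. These multiples assume that the single-dose fold-change carries over to this population and to daily dosing, and that exposure is proportional to dose outside the stated 420-840 mg/day range. The gap does not depend on the exact fold. Starting at 140 mg would bring total exposure to about 2.7 times that intended, close to what the protocol already accepts for class A and within the range of doses it cites.

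A reader might infer that 420 mg is shown to be harmful in class B. It is not: safety at that exposure is unsupported by the documents, which is a weaker statement. With frequency unknown as well, the point does not amount to a mandatory correction.

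**What to change.** Add to section 3.2, with a cross-reference in 3.3.2.3:

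- Participants who are Child-Pugh class B at baseline (Appendix J) start at 140 mg daily, with no increase while class B persists. This should take precedence over the re-escalation option in 3.3.2 and the return to 420 mg after an antifungal is stopped (3.2.1, 14.1.7).
- Class B participants who need voriconazole or posaconazole are not enrolled, because no dose level below 140 mg exists.

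Name albumin in section 2.2.2.2 so that the class can be scored at screening; INR is already listed.

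Excluding class B altogether is an alternative for the sponsor to weigh against its conflict with the bilirubin limit. The hold in 3.3.2.3 should stay on direct bilirubin. Moving it to total bilirubin might look like a tidy alignment with the eligibility criterion, but it could put a participant enrolled near 3 x ULN on hold after a slight rise.

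The cost is a few lines of amendment. An unquantified number of participants, probably small, would start at a lower dose or, if they need those azoles, would not enrol. Those starting at 140 mg have no lower level to step down to, so the amendment should say how Table 1 applies to them.

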2.1.3 Recruitment Strategies

This protocol may be abstracted into a plain language announcement posted on NIH websites (i.e., [clinicaltrials.gov](#)) and on NIH social media platforms.

2.2 SCREENING EVALUATION

2.2.1 Screening activities performed prior to obtaining informed consent

Minimal risk activities that may be performed before the subject has signed a consent include the following:

- Email, written, in person or telephone communications with prospective subjects
- Review of existing medical records to include H&P, laboratory studies, etc.
- Review of existing MRI, x-ray, or CT images
- Review of existing photographs or videos
- Review of existing pathology specimens/reports from a specimen obtained for diagnostic purposes

2.2.2 Screening activities performed after a consent for screening has been signed

The following activities will be performed only after the subject has signed the consent for this study for screening. Screening studies must be completed within 14 days prior to enrollment unless otherwise specified below. Assessments performed at outside facilities within the timeframes below may also be used to determine eligibility once a participant has signed the consent.

2.2.2.1 Clinical Assessments

- Karnofsky performance score ([Appendix B](#)).
- Physical examination to include: general appearance of the subject, height and weight, and examination of the skin, eyes, ears, nose, throat, lungs, heart, abdomen, extremities, musculoskeletal system, nervous system, and lymphatic system. Vital signs will include blood pressure, heart rate, respiratory rate, and body temperature.
- Medical history and Demographics
- prior and concomitant medications
- Moderate or severe chronic GvHD via Chronic GvHD Assessment:
 - Diagnostic Criteria for Chronic GvHD ([Appendix A](#))
 - NIH Organ Specific Staging and Global Scoring of Chronic GvHD ([Appendix D](#) and [Appendix E](#))

